5.3. Dose modifications

During the study period, dose modifications of the investigational drug can be made based on its toxic side effects, including: dose interruption, dose reduction, modification of administration mode, and dose termination.

Dose interruption is allowed for SHR-1210, with a maximum allowable drug interruption of 12 weeks.

In addition to dose interruption, for subjects whose weight decreases to below 50 kg during the treatment period, the dose of SHR-1210 may be down-titrated to 3 mg/kg q2w, as appropriate.

Dose modifications due to apatinib-related toxicity include: dose interruption, dose reduction, modification of administration mode (first modification: 5 days on treatment and 2 days off; second modification: 7 days on treatment and 7 days off), and dose termination. During the study, after adjusting the administration mode of apatinib, the recovery of dose mode will not be allowed.

During the study, if definite apatinib-related AEs occur, such as hypertension, proteinuria, hand and foot syndrome (HFS), apatinib administration may be down-titrated or interrupted. After toxicity recovery, the original dose, adjusting the administration method, or terminating the dose may be given as appropriate. After discontinuing apatinib, the study subjects may continue to receive SHR-1210 monotherapy.

During the study, if immune-related toxicities occur, such as immune pneumonia,

hepatitis, enteritis, the administration of SHR-1210 and apatinib should be suspended as appropriate. Once the toxicity has recovered to \leq grade 1 or baseline levels (for the increase of laboratory parameters such as ALT/AST and total bilirubin [TBIL]), the medication can be resumed. The administration of SHR-1210 should be resumed first, and after 14 days of observation without significant abnormalities, the administration of apatinib can be initiated and the mode of subsequent administration of apatinib will be adjusted.

During the study, if \geq grade 3 immune pneumonia, \geq grade 3 TBIL increased, grade 4 ALT/AST increased, or other grade 4 immune-related toxic reactions, grade 4 injection reactions occur, or if the immune-related toxicity causes a temporary suspension of SHR-1210 administration for more than 12 weeks and still cannot recover to \leq grade 1 or baseline level, SHR-1210 must be permanently discontinued.

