8.3. Infusion reactions

Investigators need to closely monitor the possible infusion-related and/or allergic reactions, especially acute immune-mediated adverse reactions (including cytokine storms), throughout the study.

In general, prophylaxis is not required before the infusion of SHR-1210. Based on the published literature, allergic reactions/events are most likely to occur within 24 hours of infusion. If this occurs, the infusion should be slowed down or interrupted according to the situation, clinical supportive treatment should be provided, and

prophylactic medication should be administered before future treatments. Possible allergic reactions may manifest as fever, cold intolerance, chills, headache, rash, pruritus, joint pain, hypotension/hypertension, or bronchospasm. All grade 3 or 4 infusion reactions should be reported according to the SAE reporting procedures.

9. Recommendations for Management of Adverse Events

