9.3. Infusion reactions

Since SHR-1210 is a fully humanized monoclonal antibody, it is unlikely to cause infusion reactions, and no prophylactic medication is required before infusion. If an infusion reaction occurs, it should be managed according to the situation by slowing down or interrupting the infusion, providing clinical supportive care, and administering prophylactic medication before subsequent treatments. Acute infusion reactions (including cytokine release syndrome, vascular edema, anaphylactic shock, and allergic reactions, please refer to NCI CTCAE v4.03 criteria) usually occur at the time of infusion or shortly after drug infusion, with symptoms and signs typically disappearing within 24 hours after the infusion is completed. Symptoms and signs include:

Allergic reactions/hypersensitivity reactions (including drug-induced fever), cough, cold intolerance, chills/shivering, dizziness, headache, fatigue (asthenia, somnolence), rash/peeling, pruritus cutaneous/pruritus, joint pain, muscle pain, hypotension or hypertension, nausea, vomiting, sweating (diaphoresis), tachycardia, tumor pain, urticaria (rubella), dyspnea (shortness of breath) or bronchospasm. All grade 3 or 4 infusion reactions should be reported to the sponsor within 24 hours, and if they meet the criteria for SAEs, they should be reported as SAEs. The management of allergic reactions should be based on the medical practice and guidelines of the study site. The

following are treatment recommendations for infusion reactions, for reference.

Table 5 Recommendations for Infusion Reactions Treatment

CTCAE Grade	Clinical Symptoms	Clinical Management	SHR-1210 Treatment
Grade 1 (mild)	Mild transient reaction;	Bedside observation, close monitoring until recovery. (Subsequently, it is recommended to administer prophylactic medication before infusion: at least 30 minutes prior to SHR-1210 administration, diphenhydramine 50 mg or equivalent, and/or acetaminophen 325 ~ 1000 mg)	Continue

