Grade 2 (moderate)	Moderate reactions, therapy or infusion interruption indicated but respond promptly to symptomatic treatment (e.g., antihistamines, NSAIDS,	Intravenous infusion of normal saline, diphenhydramine 50 mg IV or equivalent and/or acetaminophen 325 ~ 1000 mg; Bedside observation, close monitoring until recovery. According to clinical needs, corticosteroids or bronchodilators may be considered; The amount of study drug infused should be recorded in the original medical records;	Suspend treatment. When resuming administration after symptom disappearance, use 50% of the initial infusion rate. If no complications occur within 30 minutes, the

	narcotics, bronchodilators, intravenous infusion etc.)	Subsequently, it is recommended to administer prophylactic medication before infusion: at least 30 minutes prior to SHR-1210 administration, diphenhydramine 50 mg or equivalent, and/or acetaminophen 325 ~ 1000 mg. If necessary, hormone cortisol can be used (at a dose equivalent to a 25 mg of hydrocortisone).	infusion rate can be increased to 100% of the original rate. Closely monitor the patient. If symptoms reoccur after resolution, do not administer the current infusion of SHR-1210.
≥ Grade 3 (severe)	Grade 3: severe reactions, which do not respond to therapy and/or dose interruption; or the symptoms reoccur after resolution; sequelae requiring	Grade 3: severe reactions, which do not respond to therapy and/or dose interruption; or the symptoms reoccur after resolution; sequelae requiring	Immediately discontinue infusion of SHR-1210; Permanently discontinue. Initiate intravenous infusion of normal saline. • Bronchodilators: subcutaneous injection of 1:1000 epinephrine solution at a dose of 0.2 ~ 1 mg, or slow intravenous injection of 1:10000 epinephrine solution at a dose of 0.1 ~ 0.25 mg, and/or if necessary, intravenous injection of diphenhydramine 50 mg + methylprednisolone 100 mg or

	hospitalization.	equivalent drug;	
	Grade 4:	• Follow the study site's	
	Life-threatening	guidelines for treating allergic	
	g	reactions; conduct bedside	
		observation, close monitoring	
		until recovery.	

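### Section 5.3 makes permanent SHR-1210 discontinuation mandatory for infusion reactions only at grade 4, while the advisory Table 5 stops from grade 3, and no text says which governs

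*Protocol*

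**What the plan says.** **Mandatory text.** Protocol section 5.3 (Dose modifications) has one sentence listing the events after which SHR-1210 must be permanently discontinued. It includes pneumonia and raised total bilirubin from grade 3, raised ALT/AST at grade 4, and then "or other grade 4 immune-related toxic reactions, grade 4 injection reactions occur". Section 5.1.5 allows SHR-1210 only as an intravenous infusion and rules out bolus injection, so an injection reaction to SHR-1210 can only mean an infusion reaction.

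**Reaction-specific text.** Table 5 in section 9.3 sets out handling by grade. Treatment continues at grade 1. At grade 2 it is suspended and resumed at a reduced rate. In the row for grade 3 and above the instruction is "Immediately discontinue infusion of SHR-1210; Permanently discontinue".

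**Status of Table 5.** The sentence before it bases management on site practice and guidelines and describes what follows with the words "following are treatment recommendations for infusion reactions, for reference".

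Neither section refers to the other, and no sentence says which takes precedence.

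**The concern.** Whether a patient is given the antibody again after a severe infusion reaction is a safety decision, and a protocol should answer it once. Here the stricter answer is in a table labelled as reference material, and the laxer one is in the sentence that uses mandatory wording. An investigator who re-treats after a grade 3 reaction would depart from a recommendation but would not breach the mandatory stopping rule. A monitor checking compliance against 5.3 alone would have nothing to record.

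**Working it through.** There is no sample size, power or event count behind this point, so the check is a comparison of texts plus one line of date arithmetic.

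**Step 1: the thresholds side by side.**

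| Text | Force | Lowest infusion-reaction grade for a permanent stop |
|---|---|---|
| 5.3, discontinuation sentence | mandatory | 4 |
| 9.3, Table 5 | recommendation, for reference | 3 |

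The difference is 4 − 3 = 1 CTCAE grade. The group left uncovered by the mandatory rule is patients with a grade 3 infusion reaction.

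**Step 2: can both be followed?** Yes. Section 5.3 says when stopping is compulsory. It does not say that grade 4 is the only occasion for stopping, and it does not authorise re-treatment after grade 3. Stopping at grade 3 satisfies both texts. Re-treating after grade 3 satisfies 5.3 and goes against Table 5.

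**Step 3: does other text make the grade 3 stop mandatory?**

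- Section 4.3.1 lists intolerable toxicity and the investigator's opinion as grounds for stopping. These permit a stop at grade 3 but name no grade and do not compel it.
- Section 5.3 also requires a stop when immune-related toxicity has not recovered after more than 12 weeks of interruption. Section 9.3 expects infusion reactions to clear within 24 hours, so this would rarely apply.
- Section 9.1, on other immune-related adverse reactions, stops SHR-1210 permanently for severe grade 3 or grade 4 events. Section 8.3 counts acute immune-mediated reactions among infusion-related ones, so this supports a grade 3 threshold. However, the 9.1 recommendations are also introduced as being for reference, so they do not settle precedence.

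No text closes the gap.

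**Step 4: how soon would it matter?** Section 5.2 sets a 2-week interval, which is 14 days, with a window of ±3 days. If the reaction fell on the scheduled day, the next infusion is due between 14 − 3 = 11 and 14 + 3 = 17 days later. This only restates the dosing schedule, but it shows that the decision comes up quickly.

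**Step 5: how many patients?** The protocol gives no infusion-reaction rate and calls such reactions unlikely. No expected count can be derived from it.

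**The case against.** The strongest reply is that this is a coherent two-tier rule: stopping is compulsory at grade 4 and recommended at grade 3. The 5.3 sentence uses grade 3 for some toxicities and grade 4 for others, so grade 4 may have been chosen deliberately. Single-centre conduct and the 24-hour report of grade 3 and 4 reactions to the sponsor (9.3) also limit inconsistent handling. Part of this stands. The texts are compatible, the events are expected to be uncommon, and the reporting rule helps detection. However, the protocol nowhere describes a two-tier rule, Table 5 leaves no discretion at grade 3, and reporting a reaction does not decide whether SHR-1210 may be given again.

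A reader might infer more than the documents support:

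- **That the protocol contradicts itself.** It does not, for the reason in step 2.
- **That Table 1 permits resumption.** Its row for other nonhematologic toxicities lets treatment resume after grade 3 once the toxicity is at grade 1 or lower. But Table 1 is itself only recommended, that row fits infusion reactions poorly (its grade 2 entry needs at least 7 days' duration and its grade 3 entry changes the apatinib schedule), and a specific table exists.
- **That the lead-in sentences authorise re-treatment at any grade.** Section 8.3 has "prophylactic medication should be administered before future treatments" and section 9.3 has "administering prophylactic medication before subsequent treatments", neither with a grade limit. Both are general statements qualified as depending on the situation, and 9.3 then gives the grading table.
- **That the reporting rule shows grade 3 was the intended stopping threshold.** Section 8.3 says "All grade 3 or 4 infusion reactions should be reported according to the SAE reporting procedures", and 9.3 narrows this to reactions that meet the SAE criteria. Neither sentence concerns discontinuation.
- **That Table 5 conflicts with itself on recurrence.** The grade 2 cell says "If symptoms reoccur after resolution, do not administer the current infusion of SHR-1210". The next row defines grade 3 as reactions "which do not respond to therapy and/or dose interruption; or the symptoms reoccur after resolution", with a permanent stop. The first is the immediate action and the second the classification that follows. Only a cross-reference is missing.

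**Conclusion.** The point holds as an unreconciled threshold. The mandatory rule in 5.3 stops SHR-1210 permanently for infusion reactions at grade 4, the reaction-specific but advisory Table 5 stops from grade 3, and no precedence is stated. The protocol therefore does not require stopping after a grade 3 infusion reaction, although its own specific guidance says to stop. The gap is one CTCAE grade and acts on individual patients. The number affected cannot be estimated from the protocol.

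This rests on two readings: that injection reactions in 5.3 are infusion reactions, which the infusion-only route supports, and that Table 5 is advisory, which its lead-in states. The objective response rate, its confidence interval and the planned 30 patients are unaffected. The change should be made because it concerns patient safety and is cheap, not because the primary analysis is at risk.

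**What to change.** In the mandatory discontinuation sentence of section 5.3, replace the grade 4 injection-reaction item with: *grade 3 or higher infusion reactions (see Table 5)*. This adopts the protocol's own reaction-specific threshold and makes it binding. If the sponsor in fact wants to allow re-treatment after grade 3, it should say so and change Table 5 to match.

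Optional tidying in the same amendment: exclude infusion reactions from the general nonhematologic row of Table 1, refer recurrence in the Table 5 grade 2 cell to the row below, and limit the premedication sentences in 8.3 and 9.3 to grades 1 and 2.

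The cost is one phrase in a protocol amendment, with no extra patients, visits or tests. The clinical downside is small: a patient with a grade 3 reaction loses the option of premedicated re-treatment, even if benefiting, but Table 5 already advises against it.

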5.4. Management, dispensing and recovery of study drugs

In this study, the management, dispensing, and recovery of the study drugs are the responsibility of the designated study nurse at the study site. The investigator must ensure that all study drugs are used only for subjects in this study, and their dosage and administration should follow the study protocol. The expired or remaining drug solutions should be disposed of according to medical waste standards. It is prohibited to hand over the study drugs to any person not participating in the clinical study. The study drugs should be stored as per the label requirements. The investigator is responsible for monitoring the supply, use, storage of study drugs, and the disposal of remaining drugs in the clinical study.

5.5. Concomitant therapies

Concomitant therapies refer to the treatments other than the study treatment, given at the discretion of the investigator for the purpose of a subject's interests.

The concomitant medications and therapies received by the subjects within 30 days prior to the initiation of the study drugs and during the study period should be recorded in the case report form (CRF) in strict accordance with GCP requirements.

Only concomitant medications and concomitant therapies used for newly occurring or unresolved AEs related to the study treatment should be recorded if a subject discontinues the study treatment. The recording should be made until at least 30 days after the last administration.

5.5.1. Other anti-tumor / anti-cancer drugs or study drugs

During the administration of the investigational drug, the study subject will not be

allowed to receive any other anti-tumor treatments.

Concurrent use of the listed anti-tumor traditional Chinese medicines is not allowed: Huatan Huisheng tablets, Yadanziyou soft capsules, Zhemu sugar syrup, Banmao, Huachansu, Chansu, Kang'ai injection, Kanglaite, Zhongjiefeng injection, Aidi injection, Awei Huapi plaster, Kangaiping pills, Fukang capsules, Xiaoaiping, Pingxiao capsules, Pingxiao tablets, Candan Sanjie capsules, Ankangxin capsules, Bosheng Aining, zedoary turmeric oil and glucose injection, Kanglixin capsules, Cidan capsules, Huaier granules, Delisheng injection, and other traditional Chinese medicine preparations that explicitly state "anti-tumor" effects in their package inserts.

5.5.2. Supportive care

Palliative and supportive care for disease-related symptoms will depend on the investigator's judgment and relevant guidelines.

During the treatment period, the subjects should be given the best supportive care. The clinical comorbidities and various adverse reactions should be actively treated and managed, especially for the immune-related adverse reactions.

5.5.3. Immunologic agents

Concurrent use of thymalfasin, interferon, interleukin-2, and other immunologic agents is not permitted in this study.

5.5.4. Drugs with potential drug-drug interactions with apatinib

In vitro studies have shown that apatinib is primarily metabolized by the hepatic P450 enzyme CYP3A4 and has strong inhibitory effects on CYP3A4 and CYP2C9, as well as moderate inhibitory effects on CYP2C19. During treatment, the CYP3A4 inducers (dexamethasone, carbamazepine, rifampin, and phenobarbital) should be used with caution and strong CYP3A4 inhibitors (ketoconazole, itraconazole, erythromycin, and clarithromycin) should be prohibited.

During the study period, prohibited CYP3A4 substrates (drugs with a narrow safety window and potentially severe adverse reactions when metabolism is affected) include, but are not limited to:

- Hypoglycemic agents: tolbutamide, chlorpropamide
- Ergot derivatives: dihydroergotamine, ergometrine, ergotamine, methylergonovine (potential risk of ergotism, including peripheral and cerebral ischemia caused by severe vasospasm)
- Antipsychotic drugs: pimozide (potential increased risk of QT interval prolongation)
- Antiarrhythmic drugs: amiodarone (prohibited for 6 months prior to randomization), bepridil, flecainide, lidocaine, mexiletine, quinidine, propafenone
- Immunomodulators: cyclosporine, tacrolimus, sirolimus (potential increased risk of nephrotoxicity and neurotoxicity)
- Miscellaneous: quetiapine, risperidone, clozapine, atomoxetine hydrochloride

During the study period, if warfarin is used for anticoagulation, the dosage should be considered for reduction, and close monitoring should be conducted. If necessary, discontinuation of the study drugs should be considered.

5.5.5. Drugs causing QT interval prolongation

Due to the toxic and side effects of prolonging the QT interval of tinib drugs in clinical use, drugs that prolong the QT interval should be used with caution during the study. This mainly includes, but is not limited to, the following categories of drugs:

- Antibiotics: fluoroquinolones: sparfloxacin, gatifloxacin, levofloxacin, moxifloxacin, ofloxacin, ciprofloxacin; macrocyclic lipids: erythromycin, clarithromycin, telithromycin, azithromycin, roxithromycin, metronidazole
- Antiarrhythmic drugs: quinidine, procainamide, disopyramide, flecainide,

propafenone, amiodarone, dronedarone, sotalol, dofetilide, ibutilide

- Angina pectoris relievers: ranolazine, ivabradine
- Antipsychotic drugs: risperidone, fluphenazine, droperidol, haloperidol, thioridazine, pimozide, olanzapine, clozapine
- Antifungals: voriconazole, posaconazole
- Antimalarials: mefloquine, chloroquine
- Antihistamines: terfenadine, astemizole, hydroxyzine
- Gastrointestinal drugs: antiemetics: ondansetron, granisetron, dolasetron, droperidol (0.625 to 1.25 mg may be a safe dose), hydroxyzine; prokinetic drugs: cisapride, domperidone, metoclopramide
- Antidepressants: amitriptyline, imipramine, clomipramine, dosulepin, doxepin

6. Study Procedures

Before initiating the study, patients must read and sign the currently approved ICF by the Ethics Committee (EC). All tests and study procedures will be performed according to the Study Flow Chart and will not be affected by the duration of drug discontinuation. However, changes within the test window are allowed due to festivals, holidays, or other administrative reasons.

6.1. Screening (D-21 to D-1)

Unless specifically indicated, the following screening procedures must be completed within 21 days prior to the first administration of the study drug:

[Signing Informed Consent] Before conducting any clinical study procedures, written consent must be obtained in advance.

[Demographic Data] Gender, date of birth, ethnicity, height, weight.

[Tumor History]

(1) Tumor diagnosis: Clinical diagnosis before enrollment, date of first pathological

confirmation, first pathological diagnosis, pathological grade, and clinical stage;

(2) The investigator will obtain the details of the subject's past and current melanoma disease. The CKIT/BRAF/NRAS/PDGFR gene status of the subject's tumor must be collected. If the study site cannot provide this information, the CKIT/BRAF/NRAS/PDGFR gene status of the tumor will be tested during the screening period at the study site or central laboratory.

[Past Medical History] Disease name, diagnosis date, treatment drug name, whether it is ongoing, and history of tumors other than malignant melanoma.

[Concomitant Medications] The concomitant medications and therapies will be recorded within 30 days prior to the initiation of the study drug and during the study period. Only concomitant medications and concomitant therapies used for newly occurring or unresolved AEs related to the study treatment should be recorded if a subject discontinues the study treatment. The recording should be made until at least 30 days after the last administration. If a new anti-tumor treatment is initiated within 30 days, only concomitant medications used for AEs related to the study drug should be recorded.

[Thyroid Function] FT3, FT4 and TSH.

[Pituitary-Adrenal Axis Assessment] includes adrenocorticotrophic hormone, cortisol, and follicle-stimulating hormone.

[HIV Test] HIV antibody test.

[Hepatitis Panel] Hepatitis B "two half-and-half" examination: If the test results are abnormal, HBV DNA quantification and HBsAg quantitative tests should be performed; hepatitis C virus antibody (anti-HCV): For those with positive anti-HCV antibodies, HCV RNA testing must be conducted; For subjects with abnormal baseline HBsAg, HBV DNA quantification and HBsAg quantitative tests should be performed

on Day 1 \pm 7 days every 2 cycles and at the end of the study.

[Pregnancy Test] The women of childbearing potential are required to undergo serum or urine pregnancy testing.

[Adverse Events] AEs should be recorded from the time of signing the informed consent until at least 30 days after the last administration of the drug, and followed up until the AE is resolved or stabilized. It is necessary to follow up on SAEs and immune-related adverse events (irAEs) within 90 days after the last administration of SHR-1210. If the patient starts a new anti-tumor treatment, follow-up should be performed until the initiation of the anti-tumor treatment (if it starts within 30 days after the last administration, follow-up should be performed for at least 30 days after the last administration; if it starts after 30 days, follow-up should be performed until the initiation of the anti-tumor treatment).

[Imaging Examination] The investigator will conduct imaging examinations based on the patient's condition, including enhanced CT or MRI of the lesion site, chest, abdomen, and pelvis. During the screening, subjects must undergo enhanced MRI or CT of the brain. The baseline tumor assessment during the screening can be extended to within 3 weeks before treatment. CT/MRI results obtained before signing the informed consent, as long as they meet the requirements, can be used for tumor assessment at screening. A bone scan examination is required when there is clinical suspicion of bone metastasis.

[Samples Collection for Biomarkers Analyses] The existing paraffin-embedded tumor tissue samples or the fresh biopsy specimens (soybean-sized) will be collected. At least 10 sections should be prepared, among which 3 ~ 5 sections of 3 ~ 5 μ m thickness will be used for PD-L1 determination, and 5 ~ 8 paraffin sections of 8 ~ 10 μ m thickness (no cell slides are acceptable, and paraffin rolls can be collected directly)

or fresh biopsy specimens (soybean-sized) will be used for the determination of biomarkers such as tumor mutational burden (TMB). For tumor sample collection and handling methods, please refer to the Laboratory Manual.

Unless specifically indicated, the following screening procedures must be completed within 7 days prior to the first administration of the study drug:

[Hematology] white blood cell count (WBC), absolute neutrophil count (ANC), lymphocyte count (LYM), hemoglobin (Hb), platelet count (PLT);

[Urinalysis] Urine protein and occult blood; if the semi-quantitative results show protein 2+ for two consecutive times, a 24-hour urine protein quantitative test should be performed;

[Stool Routine] If fecal occult blood is positive, a re-examination is required. If fecal occult blood remains positive after re-examination, a gastroscopy is required;

[Blood Chemistry] ALT, AST, AKP, γ -GT, LDH, creatinine, potassium, sodium, blood lipase (only performed during the screening period and when abdominal pain, bloating, or other suspected pancreatitis symptoms occur), blood amylase (only performed during the screening period and when abdominal pain, bloating, or other suspected pancreatitis symptoms occur);

[Coagulation Function] includes INR, APTT, PT, and FIB;

[Myocardial Zymogram Examination] includes CK, CK-MB, α -hydroxybutyrate dehydrogenase, LDH, AST;

[Lymphocyte Subsets] include T cell subsets (CD3+, CD4+, CD8+), natural killer cells (CD16/56+), immunoglobulins (IgG, IgA, IgM); complement (C3) (to be performed within 14 days prior to treatment);

[Vital Signs] temperature, pulse, respiratory rate, blood pressure;

[Blood Pressure Monitoring] During the screening period, the investigator or study

nurse will measure blood pressure for patients. For each blood pressure measurement, smoking and coffee consumption are prohibited within 30 minutes prior to the measurement, and the patient should rest quietly for at least 10 minutes. The measurement should be taken in a seated position, with the elbow at the same level as the heart, and blood pressure should be measured on the same side each time.

[Physical Examination] General condition, head and face, skin, lymph nodes, eyes (sclera, pupils), ears, nose, throat, oral cavity, respiratory system, cardiovascular system, abdomen (including liver and spleen), reproductive-urinary system, musculoskeletal system, nervous system, and mental status; Note: A comprehensive physical examination must be conducted during the study period, and only abnormal findings need to be recorded in the CRF. If there is no change compared with the screening period, there is no need to repeat the recording.

[ECOG Score]

[12-Lead Electrocardiogram] If any abnormalities are identified, two additional confirmations must be performed, or other necessary examinations should be conducted based on the investigator's judgment.

[Echocardiography]

[Blood Collection for Biomarkers Analyses] Ten (10) mL of patient's blood samples will be collected at baseline, processed and sent according to the Laboratory Manual. The eligibility must be rechecked, patients can only be included in the study if they meet all inclusion criteria and do not meet any exclusion criteria.

